10.3 ECG

12-lead ECGs are categorised as “normal”, “abnormal, not clinically significant” or “abnormal clinically significant”. Data will be summarised by treatment. Shift tables will be presented for changes from pre-administration (visit 5, day -1) to 12, 24 and 48h post-administration (visit 5, day 1, 2, and 3).

10.4 Adverse Events

AEs will be coded according to the latest version of the MedDRA. All data will be listed by subject. For treatment emergent AEs, the listings will include the number of days from administration of IMP until the start of the AE. Only treatment emergent AEs (TEAEs) will be presented in summary tables. All summary tables will include columns for each treatment and a total column. Separate data listing will be provided for AEs that are defined as pre-treatment or post-treatment. The following definitions will be used:

- A pre-treatment Adverse Event is an Adverse Event with start time after signing of informed consent and before administration of IMP
- A Treatment Emergent Adverse Event (TEAE) is an Adverse Event that has start time or worsens in intensity after administration of IMP and until the follow-up visit (visit 13)
- A post-treatment Adverse Event is an Adverse Event that has start time after the follow-up visit (visit 13)

If the start date of an AE is completely or partially missing, the AE will be considered treatment emergent unless it can be excluded that it was treatment emergent based on the incomplete date.

10.4.1 Overview of Treatment Emergent Adverse Events

The summary table for treatment emergent adverse events will include the number of subjects reporting an AE, the percentage of subjects (%) with an AE and the number of events reported, for each treatment and in total, for the following categories:

- All TEAEs
- Deaths
- Serious TEAEs
- Non-serious TEAEs
- Severe TEAEs
- Moderate TEAEs
- Mild TEAEs
- Adverse drug reactions (ADRs, i.e. TEAEs with reasonable possible causal relationship to IMP)
- AEs leading to withdrawal
- Other significant AEs

10.4.2 Incidence of Treatment Emergent Adverse Events

Summary tables will be prepared for the incidence of treatment emergent adverse events per treatment and in total by MedDRA system organ class (SOC) and preferred term (PT), presenting number of subjects reporting an AE, the percentage of subjects (%) with an AE and the number of events reported. Summary tables will be prepared for:

- All TEAEs
- SAEs
- TEAEs by causality (reasonable possibility/no reasonable possibility)
- TEAEs by intensity (mild/moderate/severe)
- ADRs by intensity

Supporting data listings will be provided for:

- All adverse events
- Serious adverse events
- ADRs
- Adverse events leading to death
- Adverse events leading to withdrawal
- Pre-treatment adverse events
- Post-treatment adverse events

Missing values will be treated as missing except for causality, intensity, and seriousness of an AE, at which occurrence a “worst case” approach will be taken. Thus, if causality is missing the AE will be regarded as related to the IMP, if the intensity is missing the intensity of the AE will be regarded as severe, if seriousness is missing the AE will be regarded as an SAE, and if the outcome is missing and no date of outcome is present the outcome is regarded as “not yet recovered”.

10.4.3 Serious Adverse Events, Deaths and Other Significant Adverse Events

Separate listings will be provided for SAEs, deaths and other significant AEs if any such event occurs.

Written narratives will be issued for all serious AEs (including deaths) and AEs leading to withdrawal.

10.5 Injection Site Reactions

Injection site reactions will be summarised by treatment with the number and percentage of subjects experiencing none, mild, moderate, or severe grade of redness, pain, itching, swelling, and bruising, or any of these symptoms, immediately after injection, 30 minutes after injection, 24 hours after injection, or at any of these time points.

10.6 Malfunctions of the Administration Device

The frequency of malfunctions of the administration device will be tabulated and the details of each malfunction will be listed.

10.7 Anti-FSH Antibodies

The proportion of subjects with anti-FSH antibodies as well as the proportion of subjects with anti-FSH antibodies with neutralising capacity will be tabulated for each dose group in total and for each time point.

10.8 Physical Examination

Physical examination at the screening (visit 1) and the follow-up visit (visit 13) will be listed by subject. Shift tables will be presented for changes from screening to follow-up.

10.9 Gynaecological Examination, Cytology, and Transvaginal Ultrasound

Results of gynaecological examination, cytology, and transvaginal ultrasound at the screening (visit 1), pre-administration (visit 5), and the follow-up visit (visit 13) will be listed by subject. Shift tables will be presented for changes from screening to follow-up.

11 Interim analyses

There will be no interim analyses.

12 Deviations from the protocol

No changes to the analyses described in the trial protocol are introduced, but additional details and descriptions have been added.

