Adverse drug reactions following treatment with GnRH agonists such as DECAPEPTYL Depot include, but are not restricted to, hot flushes, decreased libido, mood changes, headache, abdominal pain and menstrual disorders that may be related to the induced transient oestrogen deficiency. Functional follicular cysts may occur upon treatment with GnRH agonists, the incidence being up to 9.3 %. In this trial, the subjects will undergo an ultrasound examination prior to the administration of the investigational medicinal product (IMP), and those who have developed cysts will be withdrawn from the trial. Without gonadotropin stimulation, these cysts have virtually no clinical significance in a healthy woman.

Overall, the risks posed to the subjects participating in the trial are deemed low and ethically justifiable. For more detailed information on FE 999049 please refer to the Investigator's Brochure.

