### Visit 5 (Run-in Period and Treatment, Day -1 to Day 3)

All subjects still found eligible after the FSH analysis will be asked to return for a treatment visit (residential stay). At the arrival to the clinic on the day before the administration day (Day -1 in the run-in period), blood sampling for analysis and eligibility check of the FSH concentration, clinical chemistry, haematology, and pregnancy test, and urine sampling for urinalysis will be performed. A limited general eligibility check (inclusion/exclusion criteria), urine drug screen, alcohol breath test, vital signs, and 12-lead ECG will also be performed. A gynaecological examination and transvaginal ultrasound will be performed if not done on Days -3 or -2.

The next day (Day 1), a blood sample for assessment of the presence of anti-FSH antibodies will be collected prior to administration of FE 999049. The subject will then be randomised to and receive an abdominal subcutaneous injection of either 12, 18, or 24 µg FE 999049. Safety assessments will be performed, injection site reactions assessed, and blood samples for PK analysis collected at predetermined time-points (Table 1). On Day 3, subsequent to the 48-hour PK sampling, the blood sampling for assessment of clinical chemistry, haematology, urine sampling for urinalysis, and assessment of vital signs and ECG, the subjects will be discharged from the clinic.

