### **7.2.4 Gynaecological Examination and Transvaginal Ultrasound**

Gynaecological examination and transvaginal ultrasound will be performed at screening, before dosing (in the period Day -3 to Day -1), and at the follow-up visit. Cytology will be performed at screening if not done within 6 months prior to screening, and at the follow-up visit.

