### **9.7.3 Safety Assessments**

#### **9.7.3.1 Vital Signs**

Vital signs (blood pressure, heart rate, and body temperature) will be presented by time for each parameter and summarised by treatment. Shift tables will be presented for changes from baseline (i.e. the last assessment prior to administration) to the follow-up visit, and will be summarised by dose group.

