#### **9.7.3.8 Gynaecological Examination, Cytology, and Transvaginal Ultrasound**

Results of gynaecological examination, cytology, and transvaginal ultrasound at the screening and the follow-up visit, including changes from baseline, will be listed by subject. Observations categorised as “abnormal” will be flagged.

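### The gynaecological and ultrasound shift tables start at screening although a pre-dose examination is collected, so they cannot separate run-in changes from changes after FE 999049

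*SAP*

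**What the plan says.** SAP 10.9 treats gynaecological examination, cytology and transvaginal ultrasound together. Results at screening, "pre-administration (visit 5), and the follow-up visit (visit 13) will be listed by subject. Shift tables will be presented for changes from screening" to follow-up. Those shift tables are the only summary. The section does not say whether these tables are split by dose group.

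Protocol 9.7.3.8, on the same assessments, asks for listings: results of examination, cytology and "transvaginal ultrasound at the screening and the follow-up visit, including changes from baseline, will be listed by subject", with abnormal observations flagged. It does not say which visit is baseline. The one definition of baseline given for a safety assessment is under vital signs (Protocol 9.7.3.1), where the shift tables show "changes from baseline (i.e. the last assessment prior to administration) to the follow-up visit".

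A pre-dose examination is collected. Protocol 7.2.4 places the gynaecological examination and ultrasound at screening, "before dosing (in the period Day -3 to Day -1), and at the follow-up visit". Cytology has no pre-dose sample. The pre-dose examination need not fall at Visit 5. It may be done at Visit 4, and the Visit 5 text reads: "A gynaecological examination and transvaginal ultrasound will be performed if not done on Days -3 or -2".

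The shift tables for vital signs, laboratory values and ECG (SAP 10.1 to 10.3) all start at Day -1. The physical examination shift (SAP 10.8) starts at screening, but Protocol 7.2.5 schedules no pre-dose physical examination. Gynaecological examination and ultrasound are therefore the only assessments whose shift table passes over a pre-dose result that the trial collects.

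**The concern.** The second objective is the safety and tolerability of FE 999049, and the ovaries and pelvis are where an FSH effect is most plausible. Protocol 1.3 names ovarian enlargement and ovarian cysts among the common side effects of other FSH products. The run-in acts on the same organs: Protocol 1.3 links GnRH agonists to transient oestrogen deficiency, menstrual disorders and follicular cysts. Some women also stop combined oral contraceptives between screening and the first depot (inclusion criterion 4 and Protocol 4.3.1).

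A shift from screening to follow-up combines all of this with whatever FE 999049 does. It can mislead in both directions. A finding acquired in the run-in and unchanged afterwards is counted as a shift. A finding present at screening, gone after down-regulation and back after FE 999049 is counted as no shift.

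**Working it through.** The documents state no sample size, power or error rate for this table, so there is no planned figure to reproduce. The check compares visit timing and then follows individual patterns through the table.

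**Inputs**
- Screening: Day -63 to Day -29 (Protocol section 6, Visit 1).
- DECAPEPTYL Depot: 28±1 and 10±1 days before IMP (SAP 3.1).
- Pre-dose examination and ultrasound: Day -3 to Day -1 (Protocol 7.2.4; flow chart note a).
- Follow-up: Day 11, which is 10 days after IMP (SAP 3.1.2).
- Day numbering: IMP is given on Day 1 and Day -28 is 28 days earlier, so there is no Day 0.

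**Days spanned by each comparison** (nominal days; any postponement after a repeated FSH test is ignored)

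Days from Day -d to Day 11 = d + 10, and the share after FE 999049 = 10 / (d + 10).

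| Start of shift | Days to Day 11 | Share after FE 999049 |
|---|---|---|
| Day -63 (screening) | 63 + 10 = 73 | 10/73 = 13.7% |
| Day -29 (screening) | 29 + 10 = 39 | 10/39 = 25.6% |
| Day -3 (pre-dose) | 3 + 10 = 13 | 10/13 = 76.9% |
| Day -1 (pre-dose) | 1 + 10 = 11 | 10/11 = 90.9% |

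These are shares of calendar time. They show what the comparison contains and do not estimate how many shifts are wrongly placed.

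**What each table would show for one woman**

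| Screening / pre-dose / follow-up | Screening to follow-up | Pre-dose to follow-up |
|---|---|---|
| normal / abnormal / abnormal | shift | no shift |
| abnormal / normal / abnormal | no shift | shift |
| normal / normal / abnormal | shift | shift |

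The screening-based table cannot tell the first row from the third, and it hides the second.

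**How many women.** The documents give no rate for run-in findings that are neither cysts nor clinically significant. As an assumption only, with rates of 5% to 30% among 24 dosed women and no effect of FE 999049, the expected number of run-in shifts is 24 × 0.05 = 1.2 to 24 × 0.30 = 7.2. A pre-dose baseline removes those already present at the pre-dose examination and unchanged at Day 11.

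**What a pre-dose baseline leaves in.** From the second depot to Day 11 is 10 + 10 = 20 days (19 to 21 with the ±1 day window). That lies within the duration of a 1-month depot, so DECAPEPTYL still acts at follow-up.

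**The case against.** The strongest reply is that little harm can come from this table. It is descriptive and is labelled as screening to follow-up. With 24 women, the subject listings show all three results, so the timing of any shift can be read off. Clinically significant gynaecological findings are adverse events (Protocol 8.1.1), dated to the examination (Protocol 8.2.2) and split at IMP administration (SAP 10.4). A significant finding acquired in the run-in is therefore not treatment emergent unless it worsens. Protocol 9.7.3.8 names only screening and follow-up, so screening is a natural reading of its undefined baseline.

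Most of this stands, and it makes the point minor. It does not remove the point, because non-significant findings are not adverse events and the shift table is their only summary.

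Three stronger readings are tempting and are not supported:
- A reader might take the sentence "Functional follicular cysts may occur upon treatment with GnRH agonists, the incidence being up to 9.3" per cent as the rate of false shifts. The same section says that women who develop cysts are withdrawn before IMP, and exclusion criterion 5 removes clinically significant Day -1 findings, including ovarian cysts. Those women never enter the table.
- A reader might infer from the Visit 5 label that an examination done on Day -3 or Day -2 drops out of the listing. SAP 1.2.3 lists all subject data, and such a result is still a pre-administration result. The label is imprecise and loses no data.
- A reader might infer that run-in changes are credited to particular FE 999049 doses. SAP 10.9 does not say that its tables are by dose group and does not describe the shifts as effects of FE 999049.

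**Conclusion.** The concern holds in a limited form. For gynaecological examination and ultrasound, the planned shift tables mix run-in changes with changes after FE 999049, although the data that would largely separate them are collected. Between 74% and 86% of the interval summarised lies before dosing, against 9% to 23% with the pre-dose examination as the start.

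The number of women affected cannot be derived from the documents, and the 1.2 to 7.2 of 24 rests wholly on assumed rates. The conclusion itself rests only on the visit schedule and on the pre-dose exclusions being applied as written. Even with the better baseline, the shifts could not be attributed to FE 999049 alone, because the depot is still active and there is no untreated group. The matter is one of presentation in a descriptive safety table.

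**What to change.** In SAP 10.9:
- Define baseline for gynaecological examination and transvaginal ultrasound as the last examination before IMP (Day -3 to Day -1, at Visit 4 or Visit 5), and use that description in place of the Visit 5 label.
- Present shifts from that baseline to Visit 13, by dose group and in total.
- Present screening to pre-dose as a separate run-in shift.
- Keep cytology as screening to follow-up.
- Add a sentence saying that the pre-dose baseline reduces the DECAPEPTYL effect without removing it, and why.

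The cost is a few lines of SAP text and one extra descriptive table. No new procedure or data item is needed. Protocol 9.7.3.8 can stand: it leaves baseline open and asks only for listings, and the shift tables are already a detail added by the SAP.
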